## A. Introduction

### **A1. List of Abbreviations**

ECRC – Emergency Care Research Core  
ED – Emergency Department  
EMR – Electronic Medical Record System  
HIPAA – Health Insurance Portability and Accountability Act  
SMS – Short Message Service (texting)

### **A2. Protocol Synopsis**

This was a prospective randomized open blinded end-point (PROBE) trial that took place at a large urban Emergency Department (ED) to test if a two-way phone messaging system improved patient adherence to referral follow-up visits at outpatient clinics. The primary outcome was patient attendance for follow-up care and the secondary outcome was ED re-admissions within 4 months after initial discharge.

## B. Background & Rationale

### **B1. Background: Adherence to Follow-up Visits After Emergency Department Discharge**

Patient adherence to ED follow-up instructions and appointments varies from 26-56% [1]. According to Kangovi et al. (2012), the most common reason a patient gave for readmission to the ED was “feeling unprepared for discharge” after the first visit [2]. The transition from ED to discharge requires the patient to be responsible for following discharge instructions, obtaining prescriptions, and finding time and resources to attend follow-up visits. Readmissions to the ED are not primarily a result of lack of access to services [3], pointing attention toward follow-up communication, which can improve transition to outpatient care [4-6]. ED clinical staff try to sit down with patients after ED visits to review instructions and sometimes schedule follow-up appointments [7]. An outpatient hemodialysis clinic that tried this model found it to be successful initially, but could not afford the extra staff to sustain it.[8]

Time and money could be saved by implementing automated appointment reminders through voice or text messages. No-show patients were reduced by 10% when one primary care clinic began using a text and phone call reminder for appointments, resulting in a positive cost-benefit analysis [9]. A similar improvement in successful follow-up appointments was found in an ED setting with a diverse population [10]. Historically, successful follow-up appointment rates of patients discharged from the Barnes Jewish Hospital Emergency Department (BJH-ED) have ranged from 9% to 37.5%, the highest rate of follow-ups were for next-day appointments [11]. It’s difficult to know how much of a difference a simple appointment reminder system would make since a previous study of BJH-ED patients found the major identifiable causes for missing appointments were “other” (34%), no transportation (25%), fear of medical cost (18%), feeling better (13%), and unsure of where to go for the visit (9%) [12]. A sophisticated and robust reminder system may be capable of addressing some of these barriers.. Recently complex modalities of electronic follow-up, such as video conferencing or remote physiological monitoring [13-15] have been introduced, further complicating follow-up care adherence, especially in an ED setting.

A two-way automated SMS system that provides a way for patients to respond has shown promise in improving communication and follow-up care with complex patients, with engagement rates between 80-90% [16]. A pilot study found a two-way system helped dialysis patients improve attendance and had potential to reduce emergency hospitalization [17].

We hypothesize that a bi-directional automated text and phone system which facilitates scheduling follow-up referrals for discharged ED patients will improve follow-up adherence.

## **B2. Hypotheses**

We hypothesize that compared to standard of care, an automated bidirectional phone messaging system will: (1) improve ED patient adherence to follow-up appointments and (2) reduce ED re-admissions.

## C. Study Objectives

### **C1. Specific Aims**

The primary objective of this study is to determine whether follow-up appointment adherence is improved within 120 days after an initial discharge from the ED by using an automated bi-directional phone messaging system.

- Specific Aim 1: Did more patients successfully attend follow-up appointments?
- Specific Aim 2: Was there a reduction in ED re-admissions?

### **C2. Outcomes of Interest**

- Primary: Time to attending a follow-up visit with referred primary or specialty care within 120 days post-discharge
- Secondary:
  - Time to re-visit to the ED (BJH or other) within 120 days post-discharge.
- Tertiary:
  - Patient engagement levels with the intervention: number of successful attempts to reach participant, number of successful attempts to schedule a follow-up appointment, length of phone call to schedule an appointment, and number of successful follow-up appointments with a specialist provider versus a primary care provider.

### **D2. Key Personnel Training Certification**

All current research team members complete Washington University HIPAA and CITI training courses. They are also registered with the Washington University Human Research Protection Office at [myIRB.wustl.edu](http://myIRB.wustl.edu) and added to the study's research team prior to viewing PHI. The research assistant and medical student are given "View Only" access to the EMR to help with patient chart reviews.

#### **D4. Funding Sources and Conflict of Interest**

There is no funding being used for this research project and there are no financial conflicts of interest.

#### **E2. Data Analysis, Sample Size Estimation, and Study Power**

The sample size from the trial was determined to meet criteria to be sufficiently powered at 90% for a two-sided  $\alpha = 0.05$ , for a 10% improvement of the primary outcome. We will conduct an Intention-to-Treat analysis to test the impact of the intervention on participant follow-up attendance and ED re-admissions. We will also conduct descriptive statistics regarding user engagement.

We might experience missing outcome data if a participant set up a follow-up appointment with a provider who was not their referral provider and is not a part of the BJH EMR network or Missouri Health Connection. These appointments will not be accessible to our study team and a participant may be labeled as *non-compliant* erroneously; however, since most Missouri health clinics participate in the Missouri Health Connection, this issue will be rare and should apply to both the control and intervention arm equally.

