### ***B2. Eligibility Criteria***

#### Inclusion criteria:

1. 18 years and older.
2. Accessible SMS capable mobile phone or residential landline.
3. Able and willing to provide consent and authorize access of participant medical record for study use.
4. Able to read English or have English-speaking family member to assist with phone communications.
5. Supplied a clinical referral with recommended outpatient follow-up timeframe or date within 4 months of discharge.

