### **F4. Data Analysis, Sample Size Estimation, and Study Power**

As detailed in Section A.2 Pilot Data, we calculated that we need to recruit at least 333 participants to have a power of 90% for a two-sided  $\alpha = 0.05$ , to detect a 10% improvement of the primary outcome. As a Phase II study, we are attempting to identify the effect size of the intervention.

We obtained the estimated improvement in the primary outcome from our pilot study. The number of eligible patients in the ED over a 6-month period were approximately 21% of admitted patients. We needed a sample size of 266 patients, and anticipated that roughly 20% of participants would be lost to follow-up, which means we needed to recruit 333 participants. We calculated our sample size using the G\*Power3 program.

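### No covariate adjustment is pre-specified, although each participant's recommended follow-up interval exists before randomisation and may predict attendance; using it would add a modest amount of precision.

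*Combined protocol and SAP*

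**What the plan says.** Section E2 gives the analysis as: "We will conduct an Intention-to-Treat analysis to test the impact of the intervention on participant follow-up attendance and ED re-admissions". Section F4 adds only the sample size: "We needed a sample size of 266 patients", it was "anticipated that roughly 20% of participants would be lost to follow-up", and "we calculated that we need to recruit at least 333 participants" for 90% power, two-sided 5% significance and a 10% improvement. Neither section names a test, a model, an effect measure or a covariate. Section B6 (Randomization Method and Blinding) describes 1:1 software allocation and names no stratification factor.

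Inclusion criterion 5 in Section B2 (Eligibility Criteria) reads: "Supplied a clinical referral with recommended outpatient follow-up timeframe or date within 4 months of discharge". Section B1 (Background) gives a range of 9% to 37.5% for past attendance after discharge from this ED and says "the highest rate of follow-ups were for next-day appointments".

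Three further places bear on the point:
- Exclusion criterion 5 and Section B8 keep out patients whose appointment was already booked at discharge.
- Section B5 lists the data entered at study entry (phone number, contact method and times, clinic details) and does not list the recommended interval.
- The primary outcome is time to attendance within 120 days in Section C2, but a yes/no attendance outcome in Section F1.

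**The concern.** A baseline variable that predicts the outcome can be used to reduce the variance of the treatment comparison and to remove chance imbalance between arms. Randomisation means this can be done without material bias. Here a candidate exists for every participant, arm cannot affect it, and the protocol's own background points to it. The trial admits referral intervals from the next day to four months, so the case mix may be wide.

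Two things are at stake. One is precision, in a trial whose power falls short of 90% at every attendance rate the documents cite. The other is pre-specification: with no model named, covariates could be chosen after outcomes have been seen, and Section F3 plans an interim chart assessment after the 85th participant.

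**Working it through.** **Inputs from the documents.** 266 evaluable, 20% loss, 333 recruited (F4); 1:1 allocation (B6); historical attendance 9% to 37.5% (B1).

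**Assumptions.** The 10% improvement is read as 10 percentage points. There are two strata, next-day at 37.5% and all others at 9%. The next-day share q is not given, so it is varied. The intervention adds 10 points in each stratum.

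**1. The plan's own figure.** 266 / 0.8 = 332.5, so 333 reproduces. 266 as a total does not. Using

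n per arm = [1.96√(2p̄(1−p̄)) + 1.2816√(p₀(1−p₀)+p₁(1−p₁))]² / 0.10²,

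the total is 502 at 9% control attendance, 848 at 23.25% (the midpoint) and 1024 at 37.5%. With 133 per arm, power is about 65%, 44% and 38% respectively. A comparison of 10% with 20% gives 266 per arm. The available text states no control rate, so the intended calculation cannot be settled. This is background here; the sample size is a separate matter.

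**2. Variance with and without the interval (binary outcome).** Control attendance is p₀ = 0.375q + 0.09(1−q), and p₁ = p₀ + 0.10.
- Unadjusted: V = p₀(1−p₀) + p₁(1−p₁)
- Between-stratum part, both arms: B = 2q(1−q)(0.285)²
- Adjusted: V − B; proportion removed = B/V
- Power = Φ(0.10/√(variance/133) − 1.96)

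At q = 0.30: p₀ = 0.1755 and p₁ = 0.2755. V = 0.1447 + 0.1996 = 0.3443. B = 2 × 0.21 × 0.0812 = 0.0341. V − B = 0.3102, so 9.9% is removed. Unadjusted power is Φ(1.965 − 1.96) = 50.2%; adjusted power is Φ(2.071 − 1.96) = 54.4%.

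| Next-day share | Variance removed | Power at 266 | Power at 333 |
|---|---|---|---|
| 5% | 3.0% | 62.5% → 63.9% | 72.3% → 73.6% |
| 30% | 9.9% | 50.2% → 54.4% | 59.4% → 63.9% |
| 40% | 10.4% | 47.0% → 51.3% | 56.0% → 60.6% |
| 50% | 10.1% | 44.5% → 48.5% | 53.2% → 57.6% |

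In patients, 266/(1 − 0.030) ≈ 274 and 266/(1 − 0.104) ≈ 297, so the gain is worth about 8 to 31 extra participants. For 90% power at q = 0.30, the total falls from 724 to 652, still far above 266 or 333.

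**3. Time-to-event form.** This was simulated with 4000 runs, exponential times to 120 days, and a common hazard ratio set to give a 10-point overall difference. At 266, moving from an unstratified to a stratified log-rank test raises power from 60% to 64% (q = 0.10), 51% to 58% (q = 0.30) and 45% to 52% (q = 0.50).

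**4. Chance imbalance.** With q = 0.30 and 133 per arm, the next-day share could differ between arms by 1.96√(2 × 0.21/133) ≈ 0.11. Multiplied by 0.285, that shifts the crude difference by about 3 points, against a target of 10.

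**5. Choice of bands.** Suppose 20% are next-day at 37.5%, everyone else is at 9%, and 60% fall within 7 days. The control rate is 0.147, with variance 0.147 × 0.853 = 0.1254. Separating next-day explains 0.16 × 0.0812/0.1254 = 10.4% of control-arm variance. A band of 7 days or less averages (0.075 + 0.036)/0.6 = 18.5%, and a split at day 7 explains only 0.24 × (0.095)²/0.1254 = 1.7%. Bands that merge next-day with the rest of the first week can lose most of the gain.

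**The case against.** The strongest reply is that an unadjusted comparison is valid under randomisation, so this is a preference about efficiency, and the evidence for the predictor is thin. Section B1 concerns historical appointments. It does not say that the 9% belongs to long intervals or that attendance falls steadily with time. Patients with a booked appointment are excluded, so a recommended interval in unbooked patients is a different variable. Assigning the whole historical range to interval therefore gives a ceiling. All of this stands, and it limits the size of the claim. It does not remove the case for adjusting, because little is lost if one pre-randomisation covariate with a few levels turns out to be weak.

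It is also fair to say that the gain is not entirely free. Section B5 does not list the interval as an entered field. Criterion 5 allows a timeframe or a date, and B5 allows a second clinic, so a coding rule is needed.

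Stronger readings are tempting but not supported:
- A reader might infer that the plan has chosen an unadjusted analysis. It has not: intention-to-treat fixes who is analysed and is silent on covariates.
- A reader might take the interval as a proven strong predictor. The documents only suggest it.
- A reader might apply the control-arm explained variance to both arms and to all 333 recruits. At q = 0.30 that gives 0.0171/0.1447 = 11.8%, about 44 extra patients (333/0.882 ≈ 377) and 65% power. The intervention arm has a larger variance with the same spread between strata, so the figure is 9.9%, about 37 patients and 63.9%; and F4 plans on 266 evaluable.

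**Conclusion.** The point holds in a limited form. No covariate adjustment or stratification is pre-specified, although a plausible prognostic variable exists for every participant before randomisation. Under the two-stratum assumption, with a next-day share of 5% to 50%, adjustment removes about 3% to 10% of the variance and adds about 1 to 5 points of power for a binary outcome, or about 4 to 7 points for a stratified log-rank test in the simulated scenarios (shares of 10% to 50%).

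These are upper-end figures. They rest on assumed stratum shares, on assigning the full 9% to 37.5% range to interval, and on the assumed effect patterns (10 points in each stratum for the binary outcome, a common hazard ratio for time to event). No scenario approaches 90%, so adjustment does not repair the sample size. It is worth doing because it costs little and settles the model in advance.

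**What to change.** 1. Record the recommended follow-up interval as a baseline field, taken from the referral that criterion 5 already requires. State a coding rule: use the earliest recommended date when a range or two referrals are given. The value predates randomisation, so it can be abstracted after enrolment, by staff blind to arm.
2. Settle whether the primary outcome is the one in Section C2 or the one in Section F1.
3. For the binary outcome, pre-specify a logistic model with arm and interval, standardised to a marginal risk difference with a robust 95% CI. Keep next-day as its own category (for example next day, 2–7 days, 8–30 days, over 30 days), or model interval continuously. Report the unadjusted difference alongside.
4. If the time-to-event outcome is kept, use a log-rank test or Cox model stratified by the same groups, noting that the Cox hazard ratio is then conditional on interval.
5. Fix this before any outcome data are reviewed by arm.

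The cost is one abstracted field, one coding rule and a short addition to the analysis section. The downside is small: little is gained if the interval proves weakly prognostic.

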### F. General Assurances

The study team agrees to comply with all applicable Washington University policies and procedures, and applicable federal, state and local laws. The research will only be performed by qualified personnel. All persons assisting with the research are adequately informed about the protocol and their research-related duties and functions. We will not implement any changes in the approved IRB application without prior IRB approval.

### G. Risks and Benefits

Potential risks include possible breach of confidentiality involving PHI/study data.

Efforts will be dedicated to minimize the risk of breach of privacy. All patient information and study data will be password protected in computer files stored on Box and only shared with research team members. Participants are assigned study ID numbers that will be used to minimize risk of exposure of patient information. Data collected from the Epharmix/CareSignal Intervention Platform are deidentified before being stored in Box.

### H. Publication Plan

We will submit a manuscript describing our results within approximately 12 months of finalizing them. Any results published from this study will not contain any participant identifiers.

## A. Overview of Study

### A1. Study Design Summary

Key elements of study design under 2015040479	
Type of study	PROBE
Total N	~330
Intervention Arm	Automated text and phone messages + Standard of Care
Control Arm	No phone messages + Standard of Care
Power	90%
Hypothesis	Adherence to follow-up visits will improve in intervention arm

Data will be collected regarding scheduling and attendance of follow-up appointments by assessing an automated bi-directional text or phone intervention and reviewing patient charts [see Section C1. Intervention Treatment].

This intervention was an add-on to standard of care with the goal to research the efficacy of an automated two-way phone system in improving follow-up appointment adherence in ED discharge patients.

### A2. Epharmix/CareSignal Intervention Builder Summary

An electronic intervention platform was developed by Epharmix/CareSignal, a WUSTL IDEA Labs (ideas.wustl.edu) company, which uses an automated two-way text or phone system for various uses to supplement clinical care, such as tracking patient adherence, collecting additional data, or delivering educational follow-up. The platform is called Epharmix/CareSignal Intervention Builder and is uploaded on Washington University (WU) servers as an application. On this platform our research team has a unique account on which we built a series of messages [see Appendix 5. Pseudocode] to test our hypothesis. Automated text or phone messaging was delivered from this account to intervention participants and participant responses returned directly to this unique account, allowing research team members to supervise responses and have control over the intervention.

Epharmix/CareSignal, Inc. and Epharmix/CareSignal employees are only involved in this project as a service provider, giving WUSTL personnel access to create an account on their platform. One employee, the Chief Developer, assists in aggregating and deidentifying data from our account [see Section D3. Method of Use of Epharmix/CareSignal Intervention Builder].

## B. Pre-Enrollment, Screening, Informed Consent & Study Entry

### ***B1. Participant Identification***

The trial enrolls any interested adult who is discharged from the Barnes Jewish ED and is recommended to see a referral provider. Discharge instructions have to be complete and the patient needs to be able to use a consistent phone, have a way to understand English communication, and be capable of consenting.

### ***B2. Eligibility Criteria***

#### Inclusion criteria:

1. 18 years and older.
2. Accessible SMS capable mobile phone or residential landline.
3. Able and willing to provide consent and authorize access of participant medical record for study use.
4. Able to read English or have English-speaking family member to assist with phone communications.
5. Supplied a clinical referral with recommended outpatient follow-up timeframe or date within 4 months of discharge.

#### Exclusion criteria:

1. Unable to be contacted by a phone call and/or SMS text message, or unwilling to provide a phone number.
2. Unwilling to consent and follow the assigned regimen and complete the required follow-up.
3. Non-English speaking.
4. Neurologic, anatomic, or cognitive disorders and thus unable to consent and/or answer text messages/phone calls.
5. Already had a follow-up appointment scheduled before being discharged.

### ***B3. Screening***

Enrollment for the trial occurs on a rolling basis for a six-month period. Treating physicians in the ED identify potential participants after completing a patient's discharge and follow-up instructions. The treating physician notifies the Emergency Care Research Core (ECRC) research coordinator with the patient's name and ED room number. While the patient is in their room, the research coordinator approaches the patient to introduce the study and discuss participation.

### ***B4. Informed Consent***

The research coordinator identifies him/herself as a research staff member that is separate from clinical care. Follow-up care is not affected by a patient's choice to enroll. The research coordinator reviews the consent form [see Appendix 1. Informed Consent Form] with patients and obtains written consent along with a demographic survey [see Appendix 2. Demographic Survey].

Patients who are unsure about enrollment can take the consent form home with them and decide to join from home, but before they attend a follow-up appointment. A phone number to the study's primary contact is listed at the top of the consent form. Some patients are also contacted by phone by the research coordinator about participating in advance of a scheduled follow-up appointment. When

consent is given over the phone, the research coordinator follows the verbal consent form [see Appendix 3. Verbal Consent Document].

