#### ***B5. Study Entry***

Once a patient provides written consent, they are enrolled as a study participant. After a research coordinator obtains consent, s/he enters a participant's preferred phone number, contact method (text or phone message), and preferred contact times into the research account on the Epharmix/CareSignal Intervention Builder platform via the web portal [epx.wustl.edu](http://epx.wustl.edu). They also include the referral clinic name, clinic phone number, and clinic address that the treating ED staff instructs the patient to call for a follow-up appointment. It is possible to include more than one referral clinic if the ED staff provides a second option.

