#### ***B6. Randomization Method and Blinding***

Once a participant is added to the Intervention Builder account, the integrated software independently randomizes participants to either the control or the intervention arm. The software s randomly allocates participants in a 1:1 ratio to intervention and control arms.

Even though participants are not informed if they were enrolled in the intervention or control arm, they are capable of inferring this information (if they did or did not receive a text or phone call).

Treating clinical staff are blinded to arm allocation. They complete treatment before a participant enrolls in the study.

The research team will be blinded to arm allocation whenever possible. EMR review to identify attended follow-up appointments and ED re-visits will be completed before intervention responses are reviewed and analysis commences.

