#### **F. Data Collection and Analysis**

##### **F1. Outcome Assessments**

The outcomes of interest are:

- Primary: Participant follow-up attendance to a referral clinic or provider (compliant / non-compliant).
- Secondary:
  - Number of re-admissions to the ED (BJH or other) within 30 days and again within four months post-discharge.
- Tertiary:
  - Patient engagement levels with the intervention: number of successful attempts to reach participant, number of successful attempts to schedule a follow-up appointment, length of phone call to schedule an appointment, and number of successful follow-up appointments with a specialist provider versus a primary care provider.

To minimize bias, all clinical staff and research team members conducting patient chart reviews will be blinded to participant arm allocation [see Section B6. Randomization Method and Blinding]. We anticipate the study will have no impact on clinical workflow since the intervention will take place during a gap in clinical care when a participant is transferred between providers and we will only be completing patient chart assessments and data analysis to finalize the study.

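### ED re-visits are counted from discharge, so for patients who consent after discharge a visit made before randomisation counts as a secondary outcome event (minor dilution, not bias)

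*Combined protocol and SAP*

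**What the plan says.** **The clock.** The ED outcome is defined in three places, each time from discharge:
- A2, Protocol Synopsis: "the secondary outcome was ED re-admissions within 4 months after initial discharge".
- C2, Outcomes of Interest: "Time to re-visit to the ED (BJH or other) within 120 days post-discharge".
- F1, Outcome Assessments: "Number of re-admissions to the ED (BJH or other) within 30 days and again within four months post-discharge".

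**Entry to the trial.** B3, Screening, gives the usual route: "While the patient is in their room, the research coordinator approaches the patient to introduce the study and discuss participation". B4, Informed Consent, adds two later routes. Unsure patients "can take the consent form home with them and decide to join from home, but before they attend a follow-up appointment", and some patients are telephoned ahead of a follow-up appointment; when "consent is given over the phone, the research coordinator follows the verbal consent form".

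**Randomisation.** It comes after consent. B5, Study Entry: "After a research coordinator obtains consent, s/he enters" the contact details in the messaging platform. B6, Randomization Method and Blinding: "Once a participant is added to the Intervention Builder account, the integrated software independently randomizes participants".

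**What is not stated.** No visible section caps the delay in days or says how an ED visit before randomisation is handled. The exclusion criteria in B2 do not mention it, and B8 deals only with new symptoms before the patient leaves the ED. The consent forms, the timeline and the pseudocode are not shown, so a limit could sit there.

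**The concern.** A patient who joins after discharge has a stretch of outcome time before allocation. An ED visit in that stretch cannot be changed by the messages, yet the definitions include it.

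Under C2 (time to re-visit) it becomes the patient's event, so a later re-visit that the messages might have prevented no longer counts. Under F1 (number of re-admissions) it is added to the count. For anyone who joins after day 30, the whole 30-day window precedes randomisation.

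The ED outcome carries the second hypothesis and Specific Aim 2. At stake is a weaker and noisier comparison on that outcome.

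**Working it through.** The plan gives no figure to reproduce here. The argument rests on reading the sections together: the origin is discharge, consent may follow discharge, randomisation follows consent, and nothing visible removes the visits in between. The documents do not say outright that such a visit counts; it counts because the definition covers it.

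**Inputs for the size (all assumed; none is in the documents).** 120-day re-visit risk in control 30%. Late joiners either 10% with a 7-day delay or 20% with a 14-day delay. Hazard ratio 0.7, acting only after randomisation. Re-visit hazard either constant (s = 1) or clustered early (Weibull shape s = 0.5).

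**Model.** H(t) = 0.3567 x (t/120)^s, where 0.3567 = -ln(0.70).
- Constant: H(14) = 0.0416, H(30) = 0.0892.
- Early: H(14) = 0.1218, H(30) = 0.1783.

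**Share of control first events before randomisation** = late share x (1 - exp(-H(delay))) / (1 - exp(-H(window))).
- 20%/14 days, 120-day window, constant: 0.20 x 0.0408 / 0.30 = 2.7%. Early: 0.20 x 0.1147 / 0.30 = 7.7% (7.65% unrounded).
- 20%/14 days, 30-day window, constant: 0.20 x 0.0408 / 0.0853 = 9.6%. Early: 0.20 x 0.1147 / 0.1633 = 14.0%.

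| Late joiners | 120-day, constant / early | 30-day, constant / early | Expected patients of 333 with a visit before randomisation |
|---|---|---|---|
| 10%, 7 days | 0.7% / 2.8% | 2.4% / 5.1% | 0.7 / 2.7 |
| 20%, 14 days | 2.7% / 7.7% | 9.6% / 14.0% | 2.7 / 7.6 |

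The 30-day share is about 1.8 to 3.5 times the 120-day share, so the 30-day window in F1 is hit hardest. With a 120-day re-visit risk of 20-40% instead of 30%, the 120-day share in the 20%/14-day case is 2.6-2.9% (constant) or 7.3-8.0% (early).

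**What the definition costs in effect size (120-day, 20%/14 days).** For on-time patients the risk difference is exp(-0.7 x 0.3567) - exp(-0.3567) = 7.91 points. For late joiners, write H for H(120) and h for H(14):
- As written: exp(-h - 0.7(H - h)) - exp(-H) = 6.94 (constant) or 5.11 (early).
- Delayed entry, counting only visits after randomisation up to day 120: exp(-0.7(H - h)) - exp(-(H - h)) = 7.23 or 5.77.
- Window moved to 120 days after randomisation: the same expression with H(134) - H(14) = 7.91 or 6.16.

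The last two assume that a patient with an earlier visit stays at the same risk of another. Weighting 80% on time and 20% late:

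| Definition | Constant | Early |
|---|---|---|
| As written | 7.71 | 7.35 |
| Delayed entry | 7.77 | 7.48 |
| Window moved | 7.91 | 7.56 |

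**The case against.** The strongest reply is that this hardly matters. The visible workflow points to enrolment in the ED room, and late consent is described only for unsure patients and for some reached by phone. Every size input is assumed, and the 20%/14-day case has no support in the text. The trial is sized for the primary outcome. With 133 per arm (half of 266) and the assumptions above, power for the ED comparison is only about 31% even with no late joiners. A count from discharge is also a natural readmission measure: restarting the clock for someone who joins on day 14 would turn the 30-day count into days 14 to 44 after discharge.

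Most of this stands. It limits the severity and argues for keeping discharge as the origin. It does not supply the missing rule.

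Three stronger readings are tempting and should not be drawn:
- **Bias.** A reader might infer that the ED comparison is biased between arms. Visits before allocation are balanced by randomisation on average; they dilute and add noise.
- **Contamination of the primary outcome.** B4 requires joining before a follow-up visit is attended, so no primary event can precede enrolment. No change to the primary outcome is claimed here.
- **The whole shortfall from 7.91 points.** That value belongs to a trial with no late joiners. Under early clustering the gap to 7.35 is 0.56 points, of which moving the window recovers 0.21 and delayed entry 0.13. The rest comes from late consent itself: the messages start after part of the high-risk period has passed, and rewording cannot change that.

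**Conclusion.** The point holds on the text as a minor defect in a secondary outcome. For late joiners, the ED definitions count visits that allocation could not affect, and under C2 such a visit displaces a later one. In the scenarios examined, 0.7-7.7% of 120-day and 2.4-14.0% of 30-day control first events would precede randomisation. Correcting the definition changes the 120-day risk difference by at most 0.21 points.

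These figures rest on an assumed 30% re-visit risk, the two late-joiner scenarios, the two hazard shapes and, for the risk differences, a hazard ratio of 0.7. If few patients join late, the effect is negligible. The reading would also change if a consent form or appendix that is not shown limits late joining or excludes patients who have already returned to the ED.

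**What to change.** Add to the secondary outcome in C2 and F1, and align the synopsis in A2:

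> Only ED visits after randomisation count as outcome events; ED visits between the index discharge and randomisation are recorded as baseline data. Discharge remains the time origin, and patients who consent after discharge enter the risk set at randomisation, with post-randomisation follow-up time as the offset for visit counts.

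Report by arm the number who consented after discharge and their discharge-to-randomisation interval, so that readers can judge how much this mattered.

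**Cost.** Wording in three places. No new form is needed: the demographic survey already records the interview date and whether it was in person or by phone, and the discharge date is in the chart. Chart review is no longer than now. The price is slightly less follow-up per late joiner, and anyone who joins after day 30 contributes nothing to the 30-day count. For patients randomised in the ED almost nothing changes.
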